- **3.5.3.2. Perinatal Period.** This model will also test whether expectant mothers who receive antenatal treatment benefit more in terms of reduced depressive symptoms than mothers who receive postnatal treatment at 12-months post-randomization. A 2-group comparison with 200 per group and an assumed mean of EPDS score of 7.93 (SD=4.68) will provide 90% power, with an alpha of 0.05, to detect a mean change of 1.5 points. This allows us to detect a drop corresponding to a small effect size of 0.3 (i.e., a drop to mean 6.43 on the EPDS). The two groups' (antenatal vs. postnatal) EPDS scores at 3-months will be compared using a two-sided two-sample t-test. Change in EPDS scores over time (baseline and every 3 months, post-randomization) also will be compared using linear mixed models including the interaction between group and time. We will examine anxiety symptoms at 12-months post randomization in a linear mixed model controlling for relevant covariates including child age.

We will examine the hypothesis of whether the subset of mothers (up to 75% of the sample) who receive the antenatal treatment will benefit more in terms of improved child

outcomes at 6-24 months than mothers who receive postnatal treatment. A 2-group comparison of 238 per group (antenatal vs. postnatal) and an assumed mean on any Bayley IV raw subscale score of 100, SD=15 to assess child mental development will provide 80% power, with an alpha of 0.05 to detect a mean clinically-significant change of 3.0 units. Raw and standardized Bayley IV scores of the two groups' children (antenatal vs. postnatal) at 12 months will be compared using a two-sided, two-sample t-test.

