Health Service Utilization	Health Service Utilization Questionnaire (HSU-Q) ²³	Total score of a 16-item scale (0-32)
List of Medications	List of Medications	Self-reported list of medications
Child: Measured at 6 to 24-months post-childbirth unless otherwise indicated		
Birth Weight & Length	Retrieved from hospital chart or self-report [†]	Assessed at birth
Breastfeeding	Whether breastfeeding and if stopped age stopped ⁷	Total Number of Months
Psychosocial Stimulation	Home Observation Measurement Evaluation (HOME) ²⁶	Total score of a 45-item checklist
Child Mental Development	Bayley Child Mental Development Scales IV ²⁷	Mean continuous score of cognitive, receptive and expressive language development

* Assessment period will be extended to account for post-treatment outcomes when there are perinatal-related interruptions to treatment (e.g., giving birth, obstetrical complications, COVID-19);

Only at baseline; *Measured at 3-months post-randomization only; ****Randomly selected for supervision, rated by self, peers, expert supervisor; ¥Also measured during treatment; [†]Self-report will be used when hospital charts are external to the recruiting site.

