3.4.2.4. Analysis for Secondary Aim 3: Perinatal Period and Child Development

Another secondary aim is to explore whether the timing of the treatment (antenatal vs. postnatal) influences child mental development at 6 to 24 months post childbirth.

All child outcomes, including child mental development and the provision of psychosocial stimulation by the mother, will be compared between two groups (antenatal vs. postnatal) at 6-24 months post childbirth using a two-sample two-sided t-test. We will require a sample of 393 participants in each of the two groups to detect a mean clinically-significant change of 3.0 units with 80% power and an alpha of 0.05. Similar comparisons will be run between the primary comparison arms (SP vs NSP; in-person vs telemedicine). Sensitivity analyses will be carried out excluding those who dropped out prior and after first session to see if the results are comparable to the entire study group. We will adjust for time since treatment by including it as a variable in the regression model comparing antenatal vs. postnatal.

We will examine the hypothesis of whether the subset of mothers (up to 75% of the sample) who receive the antenatal treatment will benefit more in terms of improved child outcomes at 6-24 months than mothers who receive postnatal treatment. A 2-group comparison of 393 per group (antenatal vs. postnatal) and an assumed mean on any Bayley IV²⁷ raw subscale score of 100, SD=15 to assess child mental development will provide 80% power, with an alpha of 0.05 to detect a mean clinically-significant change of 3.0 units. Raw and standardized Bayley IV scores of

the two groups' children (antenatal vs. postnatal) at 12 months will be compared using a two-sided, two-sample t-test.

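### The Bayley-IV power inputs are attached to raw scores, and an unadjusted t-test is planned at 12 months although children are assessed anywhere from 6 to 24 months

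*Protocol*

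**What the plan says.** Protocol 3.5.3.2 (Perinatal Period) plans the child-development comparison on "an assumed mean on any Bayley IV raw subscale score of 100, SD=15". It states that 238 children per group "will provide 80% power, with an alpha of 0.05 to detect a mean clinically-significant change of 3.0 units". SAP 3.4.2.4 uses the same mean, SD, power, alpha and difference, again labels the score raw, and states 393 per group.

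The Protocol's next sentence reads "Raw and standardized Bayley IV scores of the two groups' children (antenatal vs. postnatal) at 12 months will be compared", by a two-sided two-sample t-test. The SAP repeats it.

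On assessment age, SAP Table 2 has "Child: Measured at 6 to 24-months post-childbirth unless otherwise indicated". Protocol Table 6, Protocol 3.5.2 and the opening of SAP 3.4.2.4 use the same 6-to-24-month window, and the hypothesis in both documents is set over that window.

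On adjustment, the t-tests carry no covariate. Protocol 3.5.2 lists child age among the possible covariates of the linear mixed models when child outcomes are assessed. SAP 3.4.2.4 does not name child age. It says instead: "We will adjust for time since treatment by including it as a variable in the regression model comparing antenatal vs. postnatal". Time since treatment is not defined.

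**The concern.** Three things do not fit together.

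- **Scale.** The documents distinguish raw from standardised scores but give one mean, one SD and one target, all under the raw label. Neither says which score decides the hypothesis, so two tests could disagree with no rule for choosing between them.
- **Age.** A single raw mean and SD is hard to defend for 6-month-olds and 24-month-olds together. The 12-month wording does not resolve this, because it contradicts the window in the same section and does not say whether 12 months is the child's age or time from some other origin.
- **Confounding.** Perinatal period is a stratification factor, not a randomised assignment (Protocol 2.8), so nothing in the design balances child age between the groups. In a raw-score t-test an age difference would be read as an effect of treatment timing. The one adjustment named in the SAP may itself compare children of different ages.

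At stake are the interpretation of a secondary aim and the power claimed for it.

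**Working it through.** **1. The plan's own figures.** Inputs, from both documents: difference 3.0, SD 15, two-sided alpha 0.05, power 80%.

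n per group = 2 × (1.960 + 0.842)² × 15² / 3² = 2 × 7.849 × 25 = 392.4, so 393. The SAP figure reproduces (power 80.1%).

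For the Protocol's 238: standard error = 15 × √(2/238) = 1.375; 3/1.375 = 2.18; power = Φ(2.18 − 1.96) = 58.8%. With 238 per group, 80% power needs a difference of 2.802 × 1.375 = 3.85, or an SD of 11.7. Variants that might explain 238 do not give it: one-sided 310; 3:1 allocation 262 in the smaller group; one-sample 197; 393 inflated for 10% or 20% dropout 437 or 492.

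**2. Age-related variance if raw scores are pooled over 6 to 24 months.** The documents give no raw-score growth rate, so these are assumptions: within-age SD 15; ages uniform over the 18-month window (age SD = 18/√12 = 5.20 months); raw score rising b points per month.

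Total SD = √(15² + (5.20 b)²), and n per group follows as in step 1.

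| b (points/month) | Total SD | n per group | Power with 393 |
|---|---|---|---|
| 0.5 | 15.2 | 405 | 78.9% |
| 1 | 15.9 | 440 | 75.5% |
| 2 | 18.2 | 581 | 63.5% |
| 3 | 21.6 | 817 | 49.4% |

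**3. Age gap under the SAP regression, counting time from enrolment.** Eligibility (Protocol Table 5, SAP Table 1) is pregnancy up to 36 weeks, or 4 to 30 weeks postpartum. Assume birth at 40 weeks. An antenatal participant enrols at least 40 − 36 = 4 weeks before birth, and a postnatal participant at least 4 weeks after. At equal time since enrolment the postnatal child is therefore at least 4 + 4 = 8 weeks (1.84 months) older.

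Bias on a raw scale at that minimum gap is 1.84 × b: 0.9, 1.8 or 3.7 points for b = 0.5, 1 or 2. It reaches the whole 3.0-unit target at b = 3/1.84 = 1.63. If raw scores rise with age, it favours the postnatal group and so works against the stated hypothesis of antenatal benefit.

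**4. How firm that gap is.** With birth at 37 weeks the minimum becomes (37 − 36) + 4 = 5 weeks. Counted from the end of treatment, the order can reverse. Protocol 2.2.2 allows sessions over four months, about 17 weeks. A woman enrolled at 36 weeks who takes that long finishes at 36 + 17 − 40 = 13 weeks postpartum. A woman enrolled at 4 weeks postpartum with six weekly sessions finishes at about 10 weeks. For that pair, the antenatal child is the older one at equal time since treatment.

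**The case against.** The strongest reply is that this is a labelling slip. Standardised scores are already planned beside raw ones, and SAP Appendix 2 lists a mean of 100 for the Bayley without calling it raw, so the power sentence may simply carry the wrong adjective. That is plausible, and it limits the damage: the age problem touches the raw-score test and any raw-score regression, not the standardised comparison. It does not say which score is decisive, nor reconcile 12 months with 6 to 24.

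A reader might also infer more than the documents support:

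- **That age spread takes the raw SD well past 15.** This depends on an unstated growth rate; at 0.5 to 1 point per month the SD is 15.2 to 15.9.
- **That the SAP adjustment makes postnatal children older by construction, by 8 weeks or even 34.** The 34 weeks is 4 weeks before birth plus entry at 30 weeks postpartum. Both figures need time counted from enrolment and birth at 40 weeks, whereas the SAP leaves the origin undefined. The adjustment also belongs to the regression, not to the t-tests.
- **That the SAP withdrew child age as a covariate.** The Protocol listed it only as a possible mixed-model covariate, and the SAP is silent.
- **That child age should replace time since treatment.** At equal child age, antenatally treated mothers are further from treatment. The swap exchanges one imbalance for another, and standardising for age already deals with age.

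**Conclusion.** The point stands on scale and assessment age: both documents are wrong as written. The power inputs carry the raw label although raw and standardised scores are treated as different, and the 12-month test contradicts the 6-to-24-month window. Followed literally, raw scores are pooled over 18 months of age with no age adjustment.

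The numerical consequence can only be given as a range, on the assumptions in the working. The bias from the SAP regression is conditional: it arises on a raw scale if time is counted from enrolment, and would then tend to hide an antenatal benefit rather than create one.

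That mean 100 and SD 15 describe the standardised score is an inference from the documents' own distinction; neither document states it. The 238 against 393 discrepancy is a separate, definite error. All of this concerns a secondary aim that the SAP words as exploratory, so it should be corrected but does not affect the primary analyses.

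**What to change.** In Protocol 3.5.3.2 and SAP 3.4.2.4:

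1. Name the age-standardised Bayley-IV score as the tested outcome for antenatal versus postnatal, say that standardised means standardised for age, and attach mean 100, SD 15 and the 3.0-unit target to it.
2. Keep raw scores descriptive, or include child age at assessment in any raw-score model. Child age, time since treatment and group are closely tied, so a raw-score model holding all three will have little independent information on each.
3. Reconcile 12 months with 6 to 24 months. If only assessments near 12 months are meant, state the origin, the window and the number of children expected.
4. Define time since treatment (from randomisation, first session or last session) and keep it as a covariate for the standardised score.
5. Reconcile the Protocol's 238 per group with the SAP's 393, which is what the stated inputs give.

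The cost is wording in two sections. Standardised scores are already planned, no new data are needed, and on an SD of 15 the SAP's 393 per group is unchanged.

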# 2 METHODS – Participants, Interventions and Outcomes

# 2.1. Participants and Setting.

N=1230 pregnant and postpartum women, aged ≥18, will be recruited from three study centers though their networks of clinics. Participants will be drawn from diverse and representative populations in Toronto, Chapel Hill, and Chicago. The flow chart (Figure 1) shows the process of recruitment and follow-up of participants in each hub. In Toronto, we will recruit from Sinai Health (SH), Women's College Hospital (WCH) and St. Michael's Hospital (SMH)—three major academic hospitals that are all affiliated with the University of Toronto, and our external referral networks. In North Carolina, we will recruit from three clinical sites affiliated with the University of North Carolina (UNC) Women's and Neuroscience Hospitals. In Chicago, we will recruit from fourteen affiliated obstetric and family medicine clinics. Our trained research assistants will approach all attending women or contact via phone for a screening. At one site (WCH), permission will first be required by a member of the participant's circle of care, will introduce the study and ask if she is interested in learning more. If the participant agrees, the trained research assistant will approach the participant in person or via phone for screen. Recruitment personnel will use established safety protocols (Appendix A - Safety Protocols and Forms). Inclusion and exclusion criteria are detailed in Table 5. Screening will take place inperson or over the phone, as determined by the referral pathway.

Table 5. Inclusion and Exclusion Criteria

INCLUSION	EXCLUSION

 
EPDS≥10
 
≥18 years
 
Pregnant up to 36 weeks or 4 to 30 weeks postpartum
 
Speaks English or (US sites) Spanish
 
	
 
Active suicidal intent (ideation and plan), active symptoms of psychosis or mania
 
Psychotropic medication dose or medication change within two weeks of enrollment or beginning treatment
 
Ongoing psychotherapy (no more than once every 8 weeks or during the duration of the intervention)
 
Active substance abuse or dependence
 
Severe fetal anomalies, stillbirth or infant death at time of enrollment for index pregnancy
 
Non-English, non-Spanish speakers
 

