#### 2.8. Randomization

All participants will be stratified by perinatal period (antenatal vs. postnatal) and then randomized within site to one of the four arms, unless restricted to two arms due to COVID-related institutional restrictions of in-person care (see section 2.2.3.2) and using a web-based randomization service as part of REDCap™. Randomization will occur only after informed consent has been obtained and all baseline measures have been completed and all inclusion/exclusion criteria verified with the participant. We will enroll equal numbers in each of the four intervention arms. This strategy allows sufficient power to determine whether NSPs are no less efficacious than specialists and telemedicine is no less efficacious than in-person treatment, respectively, in settings that collectively assure ethnic and racial diversity, as well as potential heterogeneity in age, variability in symptom severity as well as access to resources.

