#### 2.10. Economic Evaluation

We will evaluate the cost-effectiveness of non-specialist providers and telemedicine, compared to specialist providers and in-person sessions. We will undertake a cost-utility analysis conducted at the 12-month post-randomization follow-up point. The primary outcome will be quality-adjusted life years (QALYs) calculated using the EuroQol 5 Dimension 5 Level (EQ-5D-5L) measure of health-related quality of life, collected at 3, 6 and 12-months.

- **2.10.1. Economic-related data.** The primary outcome related to the economic evaluation is quality adjusted life years (QALYs) calculated using the EuroQol 5 Dimension 5 Level (EQ-5D-5L) measure of health-related quality of life. An advantage of the EQ-5D-5L is that an overall utility score of health-related quality of life can be obtained, which facilitates comparisons with other interventions and health states in other illnesses.
- **2.10.2. Service use.** The use of all health services, other than the intervention (BA), are being recorded using an adapted version of the health services utilization questionnaire (HSUQ). Data on the use of BA (number and duration of therapy contacts and with whom) will be collected from existing clinical records. This measure (*see Health Service Utilization Questionnaire, Appendix C Study Measures*, pg. 35) was adapted with reference to other measures used in perinatal depression populations and for use in Canadian and US contexts with input from service users and clinicians. It will be completed at baseline (covering the last 3 months) and each follow-up interview (covering the period since the last interview). The HSUQ records use of health services, specifically: hospital inpatient stays,

outpatient appointments, emergency department visits and ambulance contacts, and community health contacts.

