- **3.5.5.1. Cost-effectiveness analyses.** The primary economic evaluation will be a cost-utility analysis (a cost-effectiveness analysis where outcomes are measured using a utility measure) carried out at the 12-month post-randomization follow-up point with outcomes expressed in terms of QALYs based on cases with non-missing data. Costs and outcomes will be compared at 12 months and will be presented as mean values by arm with standard deviations. Mean differences and 95% confidence intervals will be obtained by non-parametric bootstrap regressions to account for the non-normal distribution of the data. A secondary analysis will be a cost-effectiveness analysis using the primary clinical outcome measure, the EPDS at 12-months post-randomization. Cost-effectiveness will be assessed using the net benefit approach with reference to Bosmans' methods for economic evaluations alongside

equivalence or noninferiority trials. Incremental cost-effectiveness ratios (ICERs) will be calculated, defined as the mean difference in cost between two groups divided by the mean difference in effect. Uncertainty will be explored using cost-effectiveness planes and cost-effectiveness acceptability curves (CEACs) based on the net-benefit approach. Cost-effectiveness planes illustrate the uncertainty around the estimates of costs and effects by plotting the bootstrapped cost and effects, with points in each quadrant indicating a different implication for economic evaluation. CEACs are an alternative to confidence intervals around ICERs and show the probability that one intervention is cost-effective compared to another, for a range of values that a decision maker would be willing to pay for a unit improvement in the outcome of interest.

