- **3.5.6.2. Sensitivity and subgroup analyses.** To explore the potential impact of excluding non-responders, we will examine the sociodemographic and clinical characteristics of those included in the analyses and those in the full sample. Further, we will rerun the primary and secondary cost-effectiveness analyses with missing total costs and outcomes imputed using multiple imputation by chained equations. We will explore the possibility of conducting subgroup analyses related to heterogeneity due to clinical severity and perinatal period (antenatal or postnatal), in line with proposed clinical analyses. We will examine geographic location by postal or zip code to explore the impact of location on various measures.
- **3.5.6.** Missing Data. Strategies to reduce missing data have been discussed above. In addition, study staff will make at least four attempts to contact patients before recording their data as missing. Multiple imputation methods will be used when rates of missing data for a variable exceed 20%. Five imputed datasets will be created and the model results averaged across the five iterations. SAS's Proc MI and Proc MIANALYZE will be used to carry out the procedures. Linear mixed models will be used to assess repeated measures outcomes. These models use maximum likelihood estimation methods that retain patients who do not have complete data across all time points. Reasons for dropout will be ascertained from clinician records or interviewing a subset of the participants who dropped out and coded. Sensitivity analyses will be carried out should missing data lead to the use of multiple imputation methods. These analyses will compare the results of the models on the imputed data to the ones with the actual missing data included. For the economic evaluation, participant health records will be accessed retrospectively to ensure that all health services accessed and costs incurred are captured. In Toronto, we will work with the Institute for Clinical Evaluative Sciences (ICES) to collect these data.

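### The 12-month cost and QALY regressions name no covariates, although perinatal period, a randomisation stratum, largely decides whether the index birth is in the cost total

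*Protocol*

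**What the plan says.** Protocol 3.5.5.1 defines the primary economic evaluation as a cost-utility analysis "carried out at the 12-month post-randomization follow-up point", restricted to cases with data. For the arm differences it says: "Mean differences and 95% confidence intervals will be obtained by non-parametric bootstrap regressions to account for the non-normal distribution of the data". It names neither covariates nor a resampling scheme.

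What enters the cost total:
- Protocol 2.10.2 covers all health services other than BA. "The HSUQ records use of health services, specifically: hospital inpatient stays", among other categories.
- Protocol 3.5.6 adds that "participant health records will be accessed retrospectively to ensure that all health services accessed and costs incurred are captured".
- Neither section excludes the delivery admission.

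Who is in the trial and how they are allocated:
- Table 5 admits women "Pregnant up to 36 weeks or 4 to 30 weeks postpartum".
- Protocol 2.8 states: "All participants will be stratified by perinatal period (antenatal vs. postnatal) and then randomized within site".
- Protocol 2.2.3.2 and SAP 1.5 describe four-arm allocation, then TM only, then 3:1 in favour of in-person, then site-specific switching between two and four arms. SAP 1.5 ends with TM only once the in-person arms are full.

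In the economic plan, perinatal period appears only in the paragraph on sensitivity and subgroup analyses (numbered 3.5.6.2), as a subgroup analysis that might be explored. The SAP has no economic section. On baseline service use, Protocol 2.10.2 says: "It will be completed at baseline (covering the last 3 months) and each follow-up interview".

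**The concern.** Twelve-month cost mixes two groups: women whose total includes a birth and women whose total does not. The factor that separates them is known at randomisation and was used to stratify it, yet the cost model as written does not use it. Two different things are at stake.

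- **NSP vs SP.** The two provider types are allocated equally in every phase, so births are balanced between them. An analysis that ignores the stratum still counts the birth/no-birth gap as random noise. The interval is then wider than the design warrants, and the acceptability curve is pulled towards 50%.
- **TM vs IP.** Stratification balances perinatal period only within a site and within a period of constant allocation ratio. Pooled over the trial, TM and IP women come from different calendar periods and sites. If the antenatal share varied across these, birth cost enters the mode difference.

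**Working it through.** The plan gives no power, SD or interval width for costs, so there is no planned figure to reproduce.

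**Step 1: timing.** Assume birth by week 42 of pregnancy. A woman enrolled at week g delivers within 42 − g weeks of randomisation: 42 − 36 = 6 weeks at the latest entry and 42 − 4 = 38 weeks for entry at week 4. Both are inside 52 weeks. Postnatal women gave birth 4 to 30 weeks before enrolment.

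**Step 2: excess width, NSP vs SP.** Inputs:
- p, the antenatal share: up to 0.75 (Protocol 3.5.3.2); 0.50 is my assumed lower value.
- D, the mean birth cost; b, its SD; s, the SD of all other 12-month costs. None is in the documents. I take b from 0.5D to D and D from 0.5s to 2s.
- Birth cost is taken as independent of other costs, which have the same mean in both strata. Arms are taken as balanced within strata.

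The average within-stratum variance is s² + p·b², because only antenatal women carry the spread of birth costs. Ignoring the stratum adds p(1−p)D². The width ratio, unadjusted to adjusted, is

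sqrt(1 + p(1−p)D² / (s² + p·b²)).

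Example with D = 2s, b = 0.5D = s, p = 0.50: sqrt(1 + 0.25×4 / (1 + 0.5×1)) = sqrt(1.667) = 1.29.

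| D | b = 0.5D, p = 0.50 | b = 0.5D, p = 0.75 | b = D, p = 0.50 | b = D, p = 0.75 |
|---|---|---|---|---|
| 0.5s | 3.0% | 2.2% | 2.7% | 2.0% |
| s | 10.6% | 7.6% | 8.0% | 5.2% |
| 2s | 29.1% | 19.5% | 15.5% | 9.0% |

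**Step 3: possible shift, TM vs IP.** Shift = D × (antenatal share in TM − antenatal share in IP), so a 5-point difference gives 0.05D and no difference gives zero.

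For scale, take the 958 TM and 268 IP women of Protocol 2.6 and let w = sqrt(s² + p·b²). The adjusted half-width is about 1.96 × w × sqrt(1/958 + 1/268) = 0.135w. A 5-point difference is then 18% of the half-width at D = 0.5w, 37% at D = w and 74% at D = 2w. Because w exceeds s, these D/w values correspond to larger D/s values.

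**Step 4: can baseline cost stand in?** Three months is about 13 weeks. The baseline look-back therefore contains the index birth for women 4 to about 13 weeks postpartum, but not for those about 13 to 30 weeks postpartum or still pregnant. High baseline cost would mean different things in the two strata, so it cannot replace the stratum.

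**The case against.** **Silence is not exclusion.** A bootstrap regression can take covariates, and the text does not call it unadjusted. Protocol 3.5.1 and SAP 3.4.1 list timing of treatment among the covariates of interest, SAP 3.4.1 adjusts for variables imbalanced at baseline, and SAP 1.2 considers site in all analyses. This stands to the extent that the exact charge is unspecified covariates. But those covariate and imbalance rules are written for the EPDS comparisons. The confounder rule in 3.5.1 requires a relation to EPDS and covers analyses described before the economic section. A possible subgroup analysis does not adjust the main result.

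**NSP vs SP is only conservative.** This stands. The estimate is unbiased, the objective is secondary and no power is claimed for it. The gain is precision.

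**The width could be overstated.** A reader might infer intervals 32-41% too wide at D = 2s. That needs b = 0, every birth costing the same. SAP Appendix 1 records caesarean delivery, NICU admission, transfusion and multiple births, so birth costs will vary, and adjustment cannot remove that spread. With b between 0.5D and D, the figure is 9-29%.

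**TM vs IP may be unaffected.** A reader might infer that the telemedicine cost difference is biased. The documents do not show this: no passage gives the antenatal share by mode, phase or site. Changing allocation ratios make a difference possible, not established.

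**The cost list is not visible.** The adapted questionnaire and list of costs are in Appendix C, which is not available here. The text points to inclusion of delivery, but whether it is itemised cannot be checked.

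**Conclusion.** The point holds as an improvement to the model specification, not as an error that invalidates the economic evaluation. The cost and QALY regressions should name a recorded stratification factor that largely determines whether a birth is in the total.

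- **NSP vs SP:** unbiased, with an interval too wide by about 2-3% (D = 0.5s), 5-11% (D = s) or 9-29% (D = 2s). This rests on the assumed ranges for p, b and D/s, on balance within strata, and on delivery costs staying in the total.
- **TM vs IP:** a shift of 0.05D per 5 points of difference in antenatal share, and none if the shares are equal.

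The percentages concern cost only. For QALYs the reason is consistency: cost and QALY are combined in the same net-benefit analysis, under the same stratified design. The direction follows from the documents; the size does not, because they give no cost data.

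**What to change.** In Protocol 3.5.5.1:

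1. Pre-specify perinatal period at randomisation and site as covariates in the bootstrap regressions for cost and QALYs, and resample within perinatal period. Site belongs there because randomisation was within site, switching was site-specific, and Protocol 2.10.3 uses different unit-cost sources in Canada and the USA.
2. For TM vs IP, add randomisation phase, defined for each site by the allocation ratio in force.
3. Use baseline HSUQ cost only with a baseline-cost-by-perinatal-period term.
4. Where the birth admission can be identified, show index-birth cost as a separate line in the cost table.

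This costs some wording and a few covariates; no new data are needed for items 1 to 3. Item 4 requires finding the birth admission in the cost data. One consequence of item 2 should be accepted knowingly: women randomised while only TM was open offer no within-phase comparison of modes, so that interval may widen. Reporting TM vs IP with and without phase would show by how much.
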